### ***B. Secondary Endpoints***

An assessment of secondary endpoints will include an analysis of the following to determine trends in the data;

1. Assessment of fusion 6 and 24 months postoperatively.
2. Pain score improvement using the VAS.
3. Physical disability score improvement using the ODI.
4. Physical-functioning improvement using the 36-Item HS.
5. Satisfaction with procedure.
6. No serious adverse event classified as related to nanOss Bioactive 3D or no device failure or subsequent intervention, excluding the removal of fixation after a solid fusion occurred.

The following additional data will be presented:

- The sample size and percentage of successfully fused segments 6 and 24 months postoperatively.
- Sample sizes and percentages of successfully fused segments for different groups based on smoking status, age, sex, BMI, the number of segments treated and whether or not an IBF device was used 24 months postoperatively.
- Demographic information will be presented as sample sizes and percentages.
- Satisfaction with procedure will be presented as sample sizes and percentages for each visit.

- Pain, physical disability and physical-functioning scores will be presented as sample sizes, means, standard deviations and ranges for each visit. The post-operative results will be compared to baseline levels.
- The proportion of clinical complications, reoperations, revisions, as well as unexpected adverse events will be calculated.

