### B. Study EndpointsN

X-rays as well as axial, coronal and sagittal CT reconstructions will be used to determine the presence of bridging bone in the posterolateral spine. The primary endpoint is treated segment fusion at 12 months post-operatively based on the following criteria:

- Presence of bridging trabecular bone; and
- < 5° Angular motion; and
- < 3 mm Translational motion.

Secondary evaluation parameters include:

1. The proportion of successfully fused treated segments 6 and 24 months postoperatively.
2. Improved postoperative pain, disability and physical-functioning scores compared to baseline values.
3. Overall satisfaction with the procedure.
4. The proportion of complications and adverse events.

---

N nanOss Bioactive 3D post-market study schedule of events

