### ***C. Recruitment of Participants***

It is estimated that there will be 50 participants total. Consented participants that drop out of the Study prior to surgery or that must be withdrawn due to eligibility conflicts that arise during surgery may be replaced, however, a new participant identification number must be reassigned.

Enrollment is competitive. Each Site is required to enroll at least 1 participant within 30 days of activation and may enroll no more than 15 participants, unless approved by the Sponsor. Each Study Site will be permitted a maximum of 1 year (from activation) to enroll their participants. Once open to enrollment, a Study Site must have consistent enrollment (or documentation of screen failures) each 30 day period. The Screening and Enrollment Log will be used as a record of site activity.

Surgeons are expected to meet the enrollment goals contained in the CSA. If enrollment goals are not met for 3 consecutive months, the Study Site will be closed and may be replaced by another Study Site (as deemed necessary by the Sponsor).

The Sponsor will permit in-office flyerso to be used to recruit participants. These must be approved by the Sponsor. The IRB is expected to review any *direct* advertising that a PI or Sub-Investigator proposes to be used to recruit participants.

---

o In-office flyers template

Notice of any financial relationship between the Sponsor and a PI or Sub-Investigator must be disclosed in the informed consent.

Participants may receive reimbursement for participating in the Study provided all appointments, procedures and forms are completed. Compensation will be in the form of a \$50 US debit card issued following the 12 month and 24 month post-operative visit. Any proposed payment should be reviewed and approved by an independent IRB/EC. The compensation or any other benefit should also be consistent with the informed consent document.

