## XIV. COMPLICATIONS AND ADVERSE EVENTS

Safety assessment involves assessment of the complications, including subsequent surgical interventions and pain and neurological complication information. Pain, neurological and function symptoms should be considered complications when a patient's complaint for any of these symptoms results in an unscheduled visit or when a patient presents with new or worsening pain, neurological, and/or function symptoms as compared to the previous visit.

All non-serious operative and post-operative complications, whether or not they are related to the device, including both observed or volunteered problems, complaints, symptoms, physical signs, or diseases which occur during participation in the Study that were not present at the baseline evaluation, or were present at baseline but have worsened, are to be recorded by the PI and reported to the Sponsor.

- These should be reported to the Sponsor **no later than ten working days after the PI learns of the event.**
- This should be reported on the Complication/Adverse Event CRF.

Any serious and unanticipated serious adverse device events that have at least a possible relationship to nanOss Bioactive 3D are to be recorded on the Complication/Adverse Event CRF and reported to the Sponsor.

- These should be reported to the Sponsor **within 24 hours** of the PI becoming aware of the event via fax or email or telephone.
- The Sponsor will immediately conduct an evaluation of the events.

The Sponsor will ensure that the event is documented by the PI and reported to the appropriate authorities as required. The Sponsor has internal advisory boards composed of physicians that are available for questions and review of such events.

- A serious adverse event (SAE) is an anticipated AE that falls into one of the following categories: (a) death, (b) life-threatening adverse experience, (c) inpatient hospitalization or prolongation of hospitalization, (d) persistent or significant disability/incapacity, (e) congenital anomaly/birth defect, (f) important medical event that may jeopardize the participant and may require medical intervention to prevent an outcome listed in a-e above, or (g) any AE associated with the use of nanOss Bioactive 3D, the specificity or severity of which is not consistent with the risk information provided.

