### B. Qualitative Measurements

Qualitative assessments shall be performed by a single, independent radiographic reviewer that is board-certified, fellowship-trained, practicing neuro- or musculoskeletal radiologist. The following qualitative assessments shall be performed by a single, independent radiographic reviewer. The reviewer shall be a board-certified, fellowship-trained, practicing neuro- or musculoskeletal radiologist.

The qualitative assessments shall be conducted at the treated segments 6, 12 and 24 (as applicable) months postoperatively:

- Left & Right Posterolateral Bridging: X-rays as well as axial, coronal and sagittal CT reconstructions, when available, will be used to determine the presence of bridging. Assessment of bridging bone across the left and right posterolateral gutter, facet joint and/or transverse processes. Each treated segment will be graded separately. Posterolateral Bridging will be graded for each side (left and right) separately, and will include the entire posterolateral gutter, from the lateral-most aspect of the transverse processes to the medial-most aspects of the facet joints. Bridging between facet joints, between transverse processes, or between facet joint and transverse process will all be considered acceptable forms of bridging.
- Interbody Bridging: X-rays as well as axial, coronal and sagittal CT reconstructions,

when available, will be used to determine the presence of bridging. Assessment of bridging bone between the involved vertebral endplates. Each treated segment will be graded separately.

- Heterotopic Ossification
- Heterotopic bone formation will be evaluated to detect bone formation in unintended locations associated with the treatment.
- Hardware Condition: Assessment of device disassembly, loosening or fracture.
- Additional Observations: Other noteworthy observations will be documented at the radiologist's discretion.

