### ***A. Risks Associated with Instrumented PLF Surgery***

As with any operation, there are potential risks associated with spinal fusions and associated instrumentation.

Some of the most common complications following posterior lumbar fusion include:

- Adverse reactions to anesthesia
- Thrombophlebitis
- Infection
- Nerve damage
- Problems with bone graft
- Instrumentation/hardware problems (migration, fracture, failure, loosening)
- Muscle disruption
- Nonunion/delayed union
- On-going pain

Other less frequent complications may include:

- Adjacent segment disease
- Bowel or bladder incontinence
- Corrosion of metal hardware
- Damage to lymphatic vessels and/or lymphatic fluid exudation
- Death
- Deep infection
- Device component fracture
- Epidural hematoma, dural tear
- Fracture of the pedicle or vertebral bone
- Hardware migration
- Hematoma or seroma at the implant site
- Hemorrhage
- Ileus
- Loss of bladder or bowel control
- Loss of fixation
- Muscle damage
- Nerve root injury
- Pain, infection or weakness from bone harvest location
- Pneumonia, bronchopneumonia or collapsed lung
- Pulmonary or systemic embolism
- Secondary surgery to remove hardware
- Stress shield bone
- Thrombosis
- Vascular injury or damage resulting in catastrophic or fatal bleeding
- Wound dehiscence

These lists describe the most common risks that could occur with this kind of surgery. There may be other risks that are not currently known.

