## XIX. STATISTICAL METHODS

### ***A. Primary Endpoint***

The primary endpoint includes successful fusion of the treated segment(s) 12 months postoperatively based on the quantitative and qualitative assessments of the x-rays and CT scan. Fusion is defined as:

1. Presence of bridging trabecular bone [i.e. presence of left posterolateral bridging AND/OR right posterolateral bridging], **AND**
2. Angular motion < 5°, **AND**
3. Translational motion < 3 mm

The sample size and percentage of treated segments successfully fused will be presented. Sample sizes and percentages of treated segments successfully fused will be presented for different groups based on smoking status, age, sex, BMI, the number of segments treated and whether or not an IBF device was used.

Non-fusion will be defined as the failure to meet any one of the above criteria for fusion.

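### Secondary item 6 joins its two safety conditions with 'or no', so scored as written a participant fails it only by having both kinds of event

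*Combined protocol and SAP*

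**What the plan says.** Section XIX.B lists six secondary endpoints, to be analysed for trends. Item 6 is the composite safety item: "No serious adverse event classified as related to nanOss Bioactive 3D or no device failure or subsequent intervention, excluding the removal of fixation". The exemption for removing fixation applies after a solid fusion. The item has no sentence saying when a participant fails it, and no stated unit or output format.

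The primary endpoint in XIX.A is written differently. Its three criteria are joined by an explicit AND, and a failure rule follows: "Non-fusion will be defined as the failure to meet any one of the above criteria for fusion".

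Safety events are also covered elsewhere:

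- Section XI.B, secondary parameter 4: "The proportion of complications and adverse events".
- Section XIX.B, last bullet: "The proportion of clinical complications, reoperations, revisions, as well as unexpected adverse events will be calculated".
- Section XIV: "Safety assessment involves assessment of the complications, including subsequent surgical interventions".
- Section XVII.A, among the common complications: "Instrumentation/hardware problems (migration, fracture, failure, loosening".
- Section XV.B, in the independent radiological review: "Hardware Condition: Assessment of device disassembly, loosening or fracture".

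None of these says how the two halves of item 6 combine.

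**The concern.** In ordinary English, 'no X or Y' means neither, and the second half of item 6 uses that form for device failure and intervention. Repeating 'no' after the first 'or' breaks the form: it creates two separate negated conditions of which one is enough. On that reading, a participant with a device failure and a reoperation meets the item as long as no serious adverse event was classified as related to the graft. The reverse also holds: a participant with a related serious adverse event meets it if nothing failed and no further intervention was needed.

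The statistics section treats its connectives as meaningful elsewhere. XIX.A uses AND where every criterion is needed and AND/OR where one side of bridging is enough. An analyst who applied the section consistently could score this 'or' as 'or'.

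At stake is the meaning of one descriptive secondary result. The study is uncontrolled and section X.B says its results will be compared with the literature, so the definition of the item should have only one reading.

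**Working it through.** The plan gives no rate, target or sample-size figure for item 6, so there is nothing to reproduce. The check is one of logic, followed by the arithmetic of one participant.

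**Definitions.** A = serious adverse event classified as related to the graft. D = device failure or subsequent intervention, not counting removal of fixation after solid fusion. Device failure and intervention together count as one kind of event.

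**Rules.**
- As written: meets = (not A) or (not D) = not (A and D).
- With 'and no': meets = (not A) and (not D) = not (A or D).

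| Pattern | As written | With 'and no' |
|---|---|---|
| Neither | meets | meets |
| A only | meets | fails |
| D only | meets | fails |
| Both | fails | fails |

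The readings differ in 2 of 4 patterns, and in both the literal reading is the favourable one. If D is split into device failure and intervention there are 8 patterns. The literal rule is met in 5 and the 'and no' rule in 1, so they differ in 4: related event only, failure only, intervention only, and failure with intervention but no related event.

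**Role of the exemption.** Under the literal rule, exempting the removal of fixation can change the result only for a participant who also has A, because anyone without A already meets the item. Under 'and no' it protects every otherwise event-free participant whose hardware is removed after fusion. The exemption has a clear purpose only under 'and no', which suggests that 'neither' was meant.

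**Size.** Let x be the number of participants with exactly one of A and D, and n the number analysed. The literal proportion minus the 'and no' proportion is x/n.
- n = 50 (section XII.C, "It is estimated that there will be 50 participants total"): 1/50 = 0.020, or 2.0 percentage points per such participant.
- n = 60 (the maximum in section XII.B): 1/60 = 0.0167, or 1.7 points.
- x = 0: no difference.

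The documents give neither event rates nor their overlap, so x cannot be estimated.

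**Whether the other outputs settle it.** The proportions in XI.B and the last bullet of XIX.B are counts of components. They do not define item 6. Separate proportions for A and D would not give the combined result either, since that depends on how often both occur in the same participant.

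**The case against.** The best reply is that this is copy-editing. Most readers would take the item to mean that neither event occurred, the exemption points the same way, and nothing suggests that the sponsor would score a related serious adverse event as a safety success. Items 1 to 5 are topic labels rather than scored definitions, and none of the listed outputs is a proportion meeting item 6. The figures of 2.0 and 1.7 points are simply 1/n and rest on an assumed reporting unit. No other secondary item has a failure rule, so its absence here is not special. The component events are largely reported elsewhere. Changing the connective would also leave the unit, the time point and the meaning of device failure unstated.

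Most of this stands, and it limits the point to minor. No safety information is lost, and a reader of the other tabulations would see most events that a literal item 6 would pass over. It does not make the wording right. Item 6, unlike items 1 to 5, does state a condition, and applying that condition as written gives the wrong answer for two event patterns. The remaining gaps in the item are separate matters that this change does not claim to close.

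**Conclusion.** The concern holds, as a minor one. As written, item 6 is failed only by a participant with both a graft-related serious adverse event and a device failure or counted intervention. No section corrects this. That 'neither' was intended is an inference, though a strong one.

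Any error from literal scoring is in the favourable direction. It equals the share of participants with exactly one kind of event, which cannot be known from the documents and may be zero. The per-participant figures assume that the item is reported as a proportion of participants, with 50 or 60 in the denominator. The primary endpoint, the planned number of participants and the component safety tabulations are not affected.

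**What to change.** In XIX.B, item 6, replace 'or no' with 'and no' and leave the rest of the item, including the exemption for removal of fixation, as it stands. Add a short clause: a participant with either kind of event alone does not meet the item. Make the change before the item is scored, so that the reading is not chosen after the results are seen.

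Optionally, report graft-related serious adverse events and device failures as separate counts beside the composite. No change of denominator is needed.

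The cost is one word and a clause, with no new data collection. The reported proportion may be less favourable than under the literal wording.

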***C. Quality Assurance of the Data***

The accuracy and quality of the data obtained from the investigators and maintained by the Sponsor will be assured through a structured program of field auditing and internal review. All data received by the Sponsor during the course of the investigation will be internally processed to assure the accuracy and quality of the data.

## XX. MONITORING

### ***A. Monitors***

The Sponsor will ensure that the Study is adequately monitored. The Sponsor will designate one or more appropriately trained and qualified individuals to monitor the Study. The monitor(s) will follow the Sponsor's established written procedures as well as those procedures that are specified by the Sponsor for monitoring the Study.

Monitors will be thoroughly familiar with the product(s), the protocol, written informed consent form and any other written information to be provided to participants, the Sponsor's SOPs, GCP, and the applicable regulatory requirement(s). Physicians, clinical research associates, paramedical personnel and nurses are acceptable to perform monitoring functions. A monitor does not need to be qualified to diagnose or treat the disease for which nanOss Bioactive 3D is intended. They will also be appropriately trained, and have the scientific and/or clinical knowledge needed to monitor the trial adequately.

### ***B. Assessment***

For the Study, the factors that will be considered in the determination of the number of monitors and the education, training or expertise necessary will include the following:

- Number of PIs conducting the Study.
- Number and location of the facilities in which the Study will be conducted.
- Type of product involved in the Study.
- Nature of the disease or condition under study.

The Sponsor may conduct an assessment visit and follow-up communication prior to initiating any Study to ensure that:

- The PI understands and accepts his/her obligation in conducting the Study.
- The PI and staff have sufficient time and access to the adequate number of patients required for the Study.
- The PI and staff understand the proper use and application of nanOss Bioactive 3D.
- The PI will permit trial-related monitoring, audits, IRB review, and regulatory inspection(s) by providing direct access to source data/documents.
- The PI understands his/her obligations for filing adverse events, annual reports and a final report to the IRB and providing the documentation to the Sponsor.
- The PI understands his/her responsibility for solicitation of Informed Consent signatures from the patients prior to the participants start in the Study.

### ***C. Monitoring***

Monitors act as the main line of communication between the Sponsor and the PI. As such, it is necessary to implement alternative training and communication methods for providing and documenting ongoing, timely training and feedback, as well as to provide notification of significant changes to Study conduct or other important information.

Study Site Monitoring will be performed centrally (to the extent appropriate and feasible) and through on-site visits. At a minimum, at least 1 annual on-site visit will take place for a Study Site with active participants until the Study is completed.

Completed CRFs may be submitted via a scan to a secure email, to a secure fax line or collected during on-site visits. If a Data Management vendor is utilized during the Study, original CRFs will be submitted via a courier service.

Throughout the course of the Study, the Sponsor and/or monitors will:

- Maintain contact with the PI and his or her staff and will conduct periodic visits to the Study Site to ensure completeness and accuracy of the data being collected, as well as any evidence which may be indicative of participant risk. Any discrepancies noted in the data will be resolved with the PI or an individual previously designated by the PI. When information is incomplete, every effort will be made to resolve it.
- Ensure that the Study is conducted in accordance with the signed CSA, the post-market protocol, and conditions, if any, imposed by the IRB and/or FDA. The Sponsor will note any noncompliance by the PI with any of these documents.
- Complete administrative and regulatory tasks as well as the collection and archiving of the required regulatory documents.
- Confirm Study Personnel included on the Delegation of Authority current curriculum vitae, licensure and training documentation, have proper licensure and/or experience and/or are trained and familiar with the laws and ethical standards governing the responsible conduct of research for the tasks assigned.
- Evaluate the quality of the overall conduct of the trial at a Study Site.
- Evaluate the accuracy and completeness of the records/CRFs/source documentation.
- Verify recorded data by reviewing source documents.
- Confirm participant eligibility.
- Verify that the initial informed consent was obtained appropriately, prior to any Study-specific procedures; the consent is dated; that the person conducting the informed consent discussion signed and dated the document; and that the date on the consent form is consistent with the Study entry date.
- Monitor data quality and potential protocol deviations.
- Collect completed CRFs and verify film transfers.
- Report of the incidence of reoperations, unexpected adverse events or complications.

